7.3.3. Subgroup Analyses for Primary Endpoint

Not applicable.

7.3.4. Sensitivity and Supportive Analyses for Primary Endpoint

Not applicable.

7.4. Analysis of Secondary Efficacy Parameters

All secondary efficacy variables will be summarized using descriptive statistics.

For categorical measurements, summary statistics will include sample size, frequency, and percentages.

7.5.1.2. Investigator's Global Assessment

The IGA is an overall eczema severity rating on a 0 to 4 scale that will be used during treatment period visits to assess a participant's face and/or neck. The grades for the IGA are shown in [Table 2](#).

Table 2: Investigator's Global Assessment

Grade	Severity	Status
0	Clear	No erythema or induration/papulation, no oozing/crusting; there may be minor residual discoloration.
1	Almost clear	There may be trace faint pink erythema, with almost no induration/papulation, and no oozing/crusting.
2	Mild	There may be faint pink erythema, with mild induration/papulation and no oozing/crusting.
3	Moderate	There may be pink-red erythema with moderate induration/papulation and there may be some oozing/crusting.
4	Severe	There may be deep or bright red erythema with severe induration/papulation and with oozing/crusting.

Source: [Food and Drug Administration 2012](#).

The IGA-TS is defined as an IGA score of 0 or 1 with ≥ 2 grade improvement from baseline for both overall and the face and/or neck region.

[REDACTED]

8. SAFETY AND TOLERABILITY

[Appendix A](#) provides a list of planned tables figures, and listings. Sample data displays are included in a separate document.

8.1. General Considerations

The analyses in this section will be provided for the FAS and OL-evaluable populations in the DBVC and OL periods. Summary tables may be replaced with listings when appropriate. For instance, an AE frequency table may be replaced with a listing if it only contains a few unique PTs reported on relatively few participants.

Unless otherwise stated, table summaries will be limited to AEs occurring within 30 days of the last application of study drug or the first application in the OL period (if available) of the study, whichever is earlier.

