8.5.1. Adverse Events

Adverse events will be monitored from the time the participant signs the ICF until at least 30 days after the last dose of study drug. Adverse events for enrolled participants that begin or worsen after informed consent should be recorded on the Adverse Events Form in the eCRF regardless of the assumption of a causal relationship with the study drug. Conditions that were already present at the time of informed consent should be recorded on the Medical History Form in the eCRF. Adverse events (including laboratory abnormalities that constitute AEs) should be described using a diagnosis whenever possible rather than by individual underlying signs and symptoms.

Adverse events will be reported by the participant (or, when appropriate, by a caregiver, surrogate, or the participant's legally authorized representative). The investigator and any qualified designees are responsible for detecting, documenting, and recording events that meet the definition of an AE or SAE and remain responsible for following-up on AEs that are serious, considered related to the study drug/procedures, or that caused the participant to discontinue the study drug. Care will be taken not to introduce bias when detecting AEs and/or SAEs.

Open-ended and nonleading verbal questioning of the participant, such as "How are you feeling?" is the preferred method to inquire about AE occurrences. Adverse events may also be detected when they are volunteered by the participant during the screening process or between visits or through physical examinations, laboratory tests, or other assessments. The definition, reporting, and recording requirements for AEs are described in Section 9.

All SAEs will be reported to the sponsor or designee within 24 hours. The investigator will submit any updated SAE data to the sponsor within 24 hours of it being available.

After the initial AE/SAE report, the investigator is required to proactively follow each participant at subsequent visits/contacts. All SAEs will be followed until resolution, stabilization, the event is otherwise explained, or the participant is lost to follow-up (as defined in Section [7.3](#)).

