8.10. Safety Follow-Up

The safety follow-up period is the interval between the EOT visit and the scheduled follow-up visit, which should occur 30 (+ 3) days after the EOT visit (or after the last dose of study drug if the EOT visit was not performed). Reasonable efforts should be made to have the participant complete the follow-up visit and report any AEs that may occur during this period. Adverse events and SAEs must be reported up until at least 30 days after the last application of study drug or until toxicities resolve, return to baseline, or are deemed irreversible, whichever is longer. Reasonable efforts should be made to have the participant complete for the follow-up visit and report any AEs that may occur during this period.

9. ADVERSE EVENTS: DEFINITIONS AND PROCEDURES FOR RECORDING, EVALUATING, FOLLOW-UP, AND REPORTING

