4. DATA HANDLING DEFINITIONS AND CONVENTIONS

4.1. Scheduled Study Evaluations and Study Periods

4.1.1. Day 1

Day 1 is the date that the first application of ruxolitinib cream or vehicle cream is administered to the participants in the specific period.

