8.2. Adverse Events

8.2.1. Adverse Event Definitions

A TEAE is any AE either reported for the first time or worsening of a pre-existing event after first application of the study drug. Analysis of AEs (as discussed below) will be limited to TEAEs, but data listings will include all AEs regardless of their timing in relation to study drug administration.

Adverse events will be tabulated by MedDRA PT and SOC. Severity of AEs will be graded using the National Cancer Institute CTCAE v5 (Grades 1 to 5). The CTCAE reporting guidelines and grading details are available on the Cancer Therapy Evaluation Program website.

The subset of AEs considered by the investigator to be related to the study drug will be considered to be treatment-related AEs. If the investigator does not specify the relationship of the AE to the study drug, the AE will be considered to be treatment-related. The incidence of AEs and treatment-related AEs will be tabulated. Serious AEs will also be tabulated.

Any missing onset date, causality, or severity must be queried for resolution. Unresolved missing causality and severity will be handled according to the following rules:

- An unresolved missing causality will be considered treatment-related.
- An unresolved missing severity will be identified as an unknown severity.

For purposes of analysis, all AEs will be considered TEAEs unless the AE can unequivocally be defined as not treatment-emergent.

Application site reaction is an AE that occurs at the site of drug application. A summary of ASRs will be provided.

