APPENDIX A. PLANNED TABLES AND FIGURES

This appendix provides a list of the planned tables, figures, and listing for the Clinical Study Report. Shells are provided in a separate document for tables that are not in the most current Standard Safety Tables v1.13.

The list of tables, figures, and listings are to be used as guidelines. Modifications of the lists that do not otherwise affect the nature of the analysis will not warrant an amendment to the SAP.

Tables

Table No.	Title	Population	Standard
Baseline and Demographic Characteristics			

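### SAP 8.1 sets one default adverse event cut-off for both study periods; it needs limiting to the double-blind tables, with separate windows stated for the open-label and combined tables

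*SAP*

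**What the plan says.** SAP Section 8.1 opens with its scope: "The analyses in this section will be provided for the FAS and OL-evaluable populations in the DBVC and OL periods". It then gives a default for AE tables, which are "limited to AEs occurring within 30 days of the last application of study drug or the first application in the OL period (if available"), with the earlier of the two governing. The sentence allows for exceptions stated elsewhere, but neither document states a different window for the OL tables or the combined tables.

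The related passages are these:

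- **SAP 5.3.2** puts into the OL-evaluable population everyone who applied ruxolitinib cream at least once in the OL period, and assigns all OL analyses to that population.
- **SAP 8.2.1** defines treatment emergence by its start only: "A TEAE is any AE either reported for the first time or worsening of a pre-existing event after first application of the study drug". It also says that "data listings will include all AEs regardless of their timing in relation to study drug administration".
- **SAP 4.1.1** makes Day 1 the date on which the "first application of ruxolitinib cream or vehicle cream is administered to the participants in the specific period". No AE rule refers to this definition.
- **SAP Appendix A** plans AE table families 3.2.1 to 3.2.15, each in three versions: DBVC period (full analysis set, FAS), OL period (OL-evaluable) and whole treatment period (FAS).
- **Protocol 8.5.1** has AEs monitored "until at least 30 days after the last dose of study drug", and **Protocol 8.10** says: "Adverse events and SAEs must be reported up until at least 30 days after the last application of study drug". These are rules for collecting and reporting events, not table windows.

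**The concern.** The cut-off makes sense for the DBVC tables: it stops a participant's double-blind record when ruxolitinib cream is applied open-label. Carried over to the OL tables, it works against them. The first OL application is where OL observation begins, and the rule uses that same date to end or shorten the window. The words allowing for participants without such a date give the OL tables no way out, because every OL-evaluable participant has one.

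Safety and tolerability is a secondary objective. As written, the event window for 30 of the 45 planned AE tables (15 OL and 15 combined) has to be inferred from the table titles, and a programmer who follows the text instead would produce OL tables that are nearly empty or cut short.

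**Working it through.** **Inputs.** SAP Section 3 gives up to 35 days of screening, 4 weeks of DBVC treatment, 4 weeks of OL treatment and 30 days (+3) of follow-up after last application. Check against the stated duration: 35 + 28 + 28 + 30 = 121 days, and 121 / 7 = 17.3 weeks, which agrees with the stated figure of approximately 17 weeks.

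**Nominal completer (assumed).** Days are numbered continuously from the first double-blind application, and cream is applied through Week 8.

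- First double-blind application: Day 1
- First OL application, s: Day 29
- Last application, e: Day 56
- Last application + 30: Day 86
- OL span: 86 − 29 + 1 = 58 days
- Whole span: 86 days

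**Reading A: the window ends at the earlier of (last application + 30 days) and first OL application.**

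- Cut-off = min(e + 30, s) = min(86, 29) = Day 29.
- OL tables keep 0 of 58 days, or 1 of 58 if the cut-off date itself counts.
- Combined tables keep 28 of 86 days (29 if the cut-off date counts), the same window as the DBVC tables. Both sets use the FAS, so one repeats the other.
- Reading last application as specific to each period does not help: for the OL period it is still Day 56, and first OL application is still earlier.

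**Reading B: the window ends 30 days after the earlier of last application and first OL application.**

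- Cut-off = min(e, s) + 30 = min(56, 29) + 30 = Day 59.
- OL tables keep Days 29 to 59, which is 59 − 29 + 1 = 31 of 58 days. They lose 58 − 31 = 27 days (Days 60 to 86), all in the post-treatment follow-up.
- Combined tables keep 59 of 86 days.
- DBVC tables would run 30 days past first OL application, so they would take in events under OL treatment.
- In general the OL days lost are (e + 30) − (s + 30) = e − s. Here that is 56 − 29 = 27.

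**Dependence on the nominal completer.** Protocol 4.1 and 6.1 make OL application as needed, stopping 3 days after lesions clear. Last application can therefore come well before Week 8, and the days lost fall with it. For example, with an assumed last application on Day 33, Reading B loses 33 − 29 = 4 days, and Reading A loses (33 + 30) − 29 = 34.

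**Tables.** 15 families × 3 versions = 45. OL and combined versions: 15 + 15 = 30.

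**With the sentence limited to the DBVC tables** and the other two sets ending at last application + 30 days, the nominal completer contributes Days 1 to 28 to the DBVC tables, Days 29 to 86 (58 days) to the OL tables and Days 1 to 86 to the combined tables. Since 28 + 58 = 86, the two periods then add up to the whole with no gap or overlap.

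**The case against.** The strongest reply is that nobody would apply the sentence this way. It allows for exceptions, the OL tables are titled for the OL period and assigned to the OL-evaluable population, Day 1 is defined by period, crossover participants get an OL safety baseline (SAP 4.1.3), and the reference to an OL application where there is one fits a rule that closes the DBVC window. A reading that nearly empties 15 planned tables is unlikely to be what was meant. This stands as evidence of intent, and it is why the point is minor. It does not supply the missing rule. A title names a period but gives no start or end date, and does not say whether the 30-day follow-up belongs to it. Appendix A describes its own lists as guidelines, and none of the period-specific passages is tied to the AE window.

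Three further objections stand. Reading A is not the only literal reading: an event cannot occur within an application, so that reading has to supply a word such as until, and Reading B follows the grammar at least as closely. The loss from the OL tables is therefore near-total on one reading and partial on the other. Next, the protocol passages on 30 days govern collection, so a short table window does not breach them. Finally, SAP 8.1 and 8.2.2 allow sparse tables to be replaced by listings, so 30 is the number of tables planned rather than the number that will necessarily appear.

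A reader might also infer that, once the cut is lifted, the combined tables will place crossover participants' ruxolitinib events under vehicle, because SAP 5.3.1 groups the FAS by the treatment applied on Day 1. The documents do not support that. SAP 5.2 defines vehicle-to-ruxolitinib as a separate OL group, and the column layouts lie elsewhere: "Shells are provided in a separate document for tables that are not in the most current Standard Safety Tables v1.13". Neither source is available here.

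**Conclusion.** The point holds as a minor error of scope in a stated rule. SAP 8.1 applies a single cut-off to AE tables for both periods, and on either grammatical reading it removes OL events from the OL and combined tables: essentially all of them if the window ends at first OL application, or those more than 30 days after first OL application if it ends 30 days after the earlier date. The figure of about 27 days under the second reading rests on a nominal completer who applies cream to Week 8, and is smaller for anyone who stops sooner.

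A reader might infer that OL safety data will be lost, or that the randomised safety comparison is compromised. Neither follows. Listings keep every AE whatever its timing, and under the probable intent (a cut for the DBVC tables only) the DBVC comparison is sound. The primary efficacy analysis and the sample size are untouched. Whether the table shells already state the right windows cannot be judged from the documents.

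**What to change.** In SAP 8.1:

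1. Limit the existing sentence to the DBVC tables, and word it so that the window ends at the earlier of 30 days after last application and first OL application.
2. State that OL tables include events with onset or worsening from first OL application to 30 days after last application.
3. State that combined tables run from first application to 30 days after last application.
4. Assign an event that starts on the date of first OL application to one named period, so that it is neither counted in both nor missed.

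The cost is three or four sentences. No new data are needed, since the protocol already has AEs collected to at least 30 days after last application.

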During the 4-week, DB VC period, participants will apply study treatment BID to all areas identified for treatment at the baseline visit even if the AD begins to improve and lesions decrease in size. The mobile healthcare provider will take comprehensive photographs for the investigator to assess the AD-affected areas for the clinician-reported assessments detailed in [Table 3](#). After all the Week 4 study assessments are complete, participants who complete the Week 4 visit with no safety concerns will continue into the 4-week, OL period and will apply ruxolitinib cream 1.5% BID only to affected areas.

Throughout the study, participants who develop additional areas of AD may treat those areas with approval from the investigator, as long as the total treated BSA does not exceed 20% and there are no safety concerns regarding the additional application of study drug. Approval to treat additional areas will occur via telemedicine visits.

If AD lesions clear during the 4-week, OL period, participants will stop treatment applications 3 days after the lesions have disappeared and record the dates of these events in their diaries. If the AD lesions recur, participants may restart treatment at home at the first sign of recurrence and record the date of study drug administration.

At Week 4, efficacy (the primary endpoint of the study) will be evaluated as the proportion of participants who achieve an EASI75 of the head and neck region. Additional efficacy assessments and patient-reported outcomes will be conducted as outlined in the SoA (see [Table 3](#)).

Participants will be assessed for safety and tolerability throughout the study by monitoring the type, frequency, and severity of AEs and measuring vital signs (see [Table 3](#)).

[Figure 1](#) presents the study design schema, and the SoA for the VC and OL periods is in [Table 3](#).

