4.2. Overall Study Duration

The study will begin when the first participant (or parent or guardian) signs the ICF (and, if needed, an assent form). The end of the study is defined as the date of the last visit of the last participant in the study or the date that the last participant has discontinued study drug and has completed applicable safety follow-up assessments or is lost to follow-up.

Participants will participate in the study for a duration of up to approximately 17 weeks as follows: up to 35 days in the screening period, 4 weeks in the DB VC period, 4 weeks in the OL period, and 30 (+ 3) days for follow-up after the last application of study drug.

A participant is considered to have completed the study if they have completed all study visits including the safety follow-up visit.

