6. STUDY TREATMENT

6.1. Study Treatments Administered

Information regarding study drug and administration is provided in [Table 5](#). Participants will record study drug administration in a daily diary.

Table 5: Study Treatment Information

	Study Treatment 1	Study Treatment 2
Study treatment name:	Ruxolitinib	Vehicle
Mechanism of action:	JAK1/2 inhibitor	NA
Dosage formulation:	Cream	Cream
Unit dose strength(s)/dosage level(s):	1.5%	NA
Route of administration:	Topical	Topical
Administration instructions:	DB VC period: Apply a thin film to affected areas identified at baseline in the morning and at least 1 hour before bedtime for 4 weeks. OL period: Apply a thin film to affected areas only in the morning and at least 1 hour before bedtime as needed for 4 weeks.	
Packaging and labeling	Ruxolitinib and vehicle will be provided in 60-g tubes. Tubes will include labeling in the local language and will comply with the legal requirements of the country.	
Storage:	Ambient (15°C-30°C/59°F-86°F)	
Status of treatment in participating countries:	Investigational	

At randomization after eligibility has been confirmed, the %BSA assessed at screening will be used by the IRT system to calculate the number of tubes of study drug to be dispensed for initial supply.

During the DB VC period, all areas identified at the baseline visit should continue to be treated through the end of the period (at Week 4) even if the area begins to improve or the AD resolves completely, unless the participant meets criteria for stopping study drug.

During the OL period, starting at the Week 4 visit, only areas with active disease need to be treated. If the lesions clear, participants should continue to apply study drug for an additional 3 days to the areas of the body where lesions were last present. After 3 days of applying study drug to area where the lesions resolved, treatment should be discontinued. If this 3-day window is during a study visit and the IGA score is 0, as assessed by the investigator, treatment is to be stopped. The date of the study visit will be recorded as the treatment cycle end date. If a lesion recurs, then treatment should be resumed at the first sign of recurrence. The start and end dates of treatment applications and/or interruptions will be captured by the participant in the electronic medication diary.

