8.2.2. Adverse Event Summaries

An overall summary of AEs by treatment group will include the following:

- Number (%) of participants reporting any TEAEs
- Number (%) of participants reporting any ASRs
- Number (%) of participants reporting any serious TEAEs
- Number (%) of participants reporting any Grade 3 or higher TEAEs
- Number (%) of participants reporting any treatment-related TEAEs
- Number (%) of participants who temporarily interrupted study drug because of TEAEs
- Number (%) of participants who permanently discontinued study drug because of TEAEs
- Number (%) of participants who had a fatal TEAE

The following summaries will be produced by MedDRA term (if 2 or fewer participants appear in a table, a listing may be appropriate):

- Summary of TEAEs by SOC and PT
- Summary of TEAEs by PT in decreasing order of frequency
- Summary of ASRs by PT in decreasing order of frequency
- Summary of Grade 3 or higher AEs by SOC and PT
- Summary of Grade 3 or higher AEs by PT in decreasing order of frequency
- Summary of serious TEAEs by SOC and PT
- Summary of serious TEAEs by PT in decreasing order of frequency
- Summary of treatment-related TEAEs by SOC and PT
- Summary of treatment-related TEAEs by PT in decreasing order of frequency
- Summary of Grade 3 or higher treatment-related TEAEs by SOC and PT
- Summary of treatment-related serious TEAEs by SOC and PT
- Summary of TEAEs with a fatal outcome by SOC and PT
- Summary of TEAEs leading to dose interruption of study drug by SOC and PT
- Summary of TEAEs leading to discontinuation of study drug by SOC and PT

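### SAP 8.1 gives participants fully clear at Week 4 a longer double-blind adverse event window, which may modestly bias the crude TEAE percentages against ruxolitinib

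*SAP*

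**What the plan says.** SAP 8.1 provides the safety analyses for the double-blind vehicle-controlled (DBVC) and OL periods. Unless otherwise stated, it restricts AE tables to events "within 30 days of the last application of study drug or the first application in the OL period (if available) of the study, whichever is" the sooner. SAP 8.2.2 reports the results as crude counts and percentages by treatment group, for example "Number (%) of participants reporting any TEAEs". The SAP plans no exposure-adjusted rate.

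Four parts of the protocol bear on when the first OL application happens:

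- **Double-blind period.** Protocol 4.2 gives "up to 35 days in the screening period, 4 weeks in the DB VC period, 4 weeks in the OL period". Protocol 6.1 keeps all baseline areas under treatment to Week 4 "even if the area begins to improve or the AD resolves completely, unless the participant meets criteria for stopping study drug", so clearing does not shorten double-blind treatment.
- **OL period.** Protocol 6.1 states: "During the OL period, starting at the Week 4 visit, only areas with active disease need to be treated". Protocol 4.1 says participants "will apply ruxolitinib cream 1.5% BID only to affected areas". Protocol 6.1 asks for three further days of cream after lesions clear and adds: "If this 3-day window is during a study visit and the IGA score is 0, as assessed by the investigator, treatment is to be stopped". Treatment resumes on recurrence. Protocol 2.2.1 describes the OL period, for the active arm, as continued treatment for those who did not reach IGA 0.
- **Text that points the other way.** Protocol Section 1 (Treatment Groups and Duration, and the note in Table 3) has participants applying cream twice daily through Week 8, with no condition on active disease.
- **AE collection.** Protocol 8.5.1 collects AEs for at least 30 days after the last dose, so the extra window can contain events.

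SAP 5.3.2 admits to the OL-evaluable population only participants with at least one OL application.

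**The concern.** A crude percentage with at least one TEAE compares two arms fairly only if both are observed for about the same time. Here the end of observation is tied to an event after randomization, the first OL application, and under Protocol 4.1 and 6.1 that depends on whether any lesion remains at Week 4. Full clearance is an intended effect of the drug, so window length may depend on arm.

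A participant who clears and never re-applies is outside the OL-evaluable population. Under SAP 8.1 that person's events after Week 4 would count in the DBVC tables as events of the randomized treatment, although they arise off treatment.

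The DBVC tables are the only vehicle-controlled AE comparison in the trial, and safety and tolerability is a secondary objective. The bias would run against ruxolitinib for a reason unrelated to toxicity.

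**Working it through.** The documents state neither a window length by arm nor a clearance rate, so there is no plan figure to reproduce. The window lengths follow from the text; everything after step 1 rests on stated assumptions.

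**Step 1. Window for one participant**

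Inputs: 4 weeks of double-blind treatment (Protocol 4.2), a Week 4 visit window of ±3 days (Protocol Table 3), and the 30-day rule (SAP 8.1).

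Window end = the earlier of (last application + 30 days) and (first OL application).

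- Active lesions at Week 4, OL cream started then: about 28 days (25 to 31).
- Fully clear at Week 4, no OL application: 28 + 30 = 58 days (55 to 61).
- Fully clear, first OL application k days after Week 4: 28 + k days.

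**Step 2. Mean window per arm**

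Let c be the share fully clear at Week 4 and E the mean extra time for a cleared participant, where extra time is the smaller of 30 days and the time to first OL application. Then mean window = 28 + c × E.

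Assumed clearance, ruxolitinib vs vehicle: 10% vs 0%, 20% vs 3%, 30% vs 5%. Assumed re-application: none within 30 days (E = 30), or exponential with mean m of 30 or 14 days, for which E = m(1 − exp(−30/m)). This gives 30(1 − exp(−1)) = 18.96 and 14(1 − exp(−30/14)) = 12.36 days.

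Example, 20% vs 3% with no re-application: 28 + 0.20 × 30 = 34.0 vs 28 + 0.03 × 30 = 28.9 days, ratio 1.18.

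**Step 3. Effect on the TEAE percentage**

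Assume the same constant hazard in both arms, with 25% risk by Day 28: hazard = −ln(0.75)/28 = 0.01027 per day. Risk by Day 58 = 1 − 0.75^(58/28) = 44.9%. TEAE % = c × (risk if cleared) + (1 − c) × 25%.

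Same example: 0.20 × 44.9 + 0.80 × 25 = 29.0% vs 0.03 × 44.9 + 0.97 × 25 = 25.6%. The ratio is 1.13 and the difference 3.4 points, with no true drug effect. When cleared participants re-apply at random times, averaging over those times lowers their risk from 44.9% to 37.9% (mean 30 days) or 33.6% (mean 14 days).

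| Re-application | Clearance | Ratio of mean windows | TEAE % | Ratio | Points |
|---|---|---|---|---|---|
| None | 10% vs 0% | 1.11 | 27.0 vs 25.0 | 1.08 | 2.0 |
| None | 20% vs 3% | 1.18 | 29.0 vs 25.6 | 1.13 | 3.4 |
| None | 30% vs 5% | 1.25 | 31.0 vs 26.0 | 1.19 | 5.0 |
| Mean 30 days | 10% vs 0% | 1.07 | 26.3 vs 25.0 | 1.05 | 1.3 |
| Mean 30 days | 20% vs 3% | 1.11 | 27.6 vs 25.4 | 1.09 | 2.2 |
| Mean 30 days | 30% vs 5% | 1.16 | 28.9 vs 25.6 | 1.13 | 3.2 |
| Mean 14 days | 10% vs 0% | 1.04 | 25.9 vs 25.0 | 1.03 | 0.9 |
| Mean 14 days | 20% vs 3% | 1.07 | 26.7 vs 25.3 | 1.06 | 1.5 |
| Mean 14 days | 30% vs 5% | 1.11 | 27.6 vs 25.4 | 1.08 | 2.2 |

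The TEAE ratio exceeds 1.10 in three of the nine cases.

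**Step 4. Size against random error**

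With 50 vs 25 participants (75 randomized 2:1, Protocol 10.1), the standard error of 29.0% vs 25.6% is √(0.29 × 0.71/50 + 0.256 × 0.744/25) = 10.8 points. The 3.4-point bias is about 0.3 standard errors.

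**Step 5. Early discontinuers**

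Someone who stops at Day 14 is counted to Day 14 + 30 = 44. Assume 5% vs 15% stop at Day 14, with clearance of 20% vs 5% and no re-application.

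- Ruxolitinib: 0.20 × 58 + 0.05 × 44 + 0.75 × 28 = 34.8 days.
- Vehicle: 0.05 × 58 + 0.15 × 44 + 0.80 × 28 = 31.9 days.

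The ratio is 1.09, against 34.0/29.5 = 1.15 without discontinuers.

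**The case against.** The strongest case against the point is that the protocol can be read so that the problem hardly arises. Section 1 has everyone applying OL cream from Week 4. Section 6.4 has tubes weighed around an application at study visits, although to affected areas. The stop rule in Section 4.1 concerns lesions that clear during the OL period, not before it. The AE tables in SAP Appendix A are titled as belonging to the double-blind period, which lasts 4 weeks. This shows that the documents conflict. It does not remove the concern, because SAP 8.1 is the only stated cut-off and nothing says that a table title overrides it.

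Three stronger readings are tempting but are not supported:

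- **A reader might infer that ruxolitinib responders in general are observed for 58 days.** The long window needs no active lesion anywhere on the body. An EASI75 responder may keep up to 25% of the baseline score and usually still has areas to treat. If the planning rates of 55% vs 15% were wrongly taken as clearance with no re-application, mean windows would be 28 + 0.55 × 30 = 44.5 vs 28 + 0.15 × 30 = 32.5 days (ratio 1.37). Those rates are for head and neck response, so this is a ceiling only.
- **A reader might infer that the rule treats the arms differently.** It is the same in both; cleared vehicle participants get the same tail. Any imbalance comes from unequal clearance, and the longer tails of early discontinuers may partly offset it (step 5).
- **A reader might infer that the two arms' percentages cannot be compared.** The AE tables are descriptive, and the bias is small against sampling error. The added days are mostly off treatment, where a constant hazard is least certain.

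**Conclusion.** The point holds in a limited form. As written, SAP 8.1 lets observation time in the only vehicle-controlled AE tables depend on a treatment outcome: about 58 days for a participant fully clear at Week 4 who applies no OL cream, and about 28 days for one with lesions. The planned crude percentages do not correct for this, and the likely direction is against ruxolitinib.

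The bias is modest: a ratio of about 1.03 to 1.19 in TEAE percentages, or 1 to 5 points. That range rests on assumed clearance rates, re-application times, a 25% Day 28 risk and a constant hazard equal in both arms. It also rests on reading Protocol 2.2.1, 4.1 and 6.1 as governing OL application. If everyone applies OL cream at Week 4, the difference between cleared and uncleared completers disappears. The reason to act is that the bias is systematic and cheap to remove, not that it threatens the trial's conclusions.

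**What to change.** 1. In SAP 8.1, for participants who continue past Week 4, end the DBVC AE window at the Week 4 (EOT1) visit date, or at the first OL application if that is earlier. Tabulate later events separately by original arm, including those of participants who never enter the OL-evaluable population.
2. Also report DBVC TEAEs per person-time, using each participant's actual window. The Week 4 cut-off is not enough alone, because early discontinuers keep their 30-day tail. Under the step 5 assumptions, mean windows after the cut would be 0.05 × 44 + 0.95 × 28 = 28.8 vs 0.15 × 44 + 0.85 × 28 = 30.4 days, a ratio of 0.95 in the other direction.
3. Reconcile Protocol Section 1 (including Table 3) with Sections 2.2.1, 4.1 and 6.1 on whether a participant clear at Week 4 applies OL cream. Which rule is right is for the sponsor to decide; the SAP needs one consistent statement.

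The cost is a short SAP edit, one changed date variable, one extra row or listing for events after Week 4, and one rate column. No new data are needed.
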